14.5 End of Study

The end of the study is defined as the date where all patients have completed their assessments and all data has been cleaned, Quality Controlled and the database is locked for analysis.

15 ACCESS TO SOURCE DATA/ DOCUMENTS

The investigator, by accepting to participate to this protocol, agrees to co-operate fully with any quality assurance visit undertaken by third parties, including representatives from the Sponsor, SCTRU or the Coordinating Centre, national and/or foreign regulatory authorities or company supplying the product under investigation, as well as to allow direct access to documentation pertaining to the clinical trial (including CRFs, source documents, hospital patient charts and other study files) to these authorised individuals.

Before a site is initiated, an agreement will be signed detailing where the source data will be recorded.

16 QUALITY CONTROL AND QUALITY ASSURANCE

Quality control will be maintained through adherence to good clinical practice (GCP) and the coordinating centre's standard operating procedures (SOP)s. The coordinating centre will monitor that CRFs are being entered remotely in a timely manner and will evaluate entered CRFs for compliance with the protocol, inconsistencies and missing data.

16.1 Monitoring Visits

We have allowed for site visits in the UK to enable monitoring by SCTRU to check patient consent forms, confirm compliance with the protocol, check the management and accountability of the trial drug, ensure adequate maintenance of trial documentation, including participants' medical records, and complete source data verification (SDV) on the patient data as defined in the Data Monitoring Plan. Higher levels of monitoring will be performed, if requested, by the Data Monitoring Committee (DMC), or if the investigators, the Trial Management group or Trial Steering Committee identify particular safety issues.

Participating centres may be monitored by SCTRU to confirm compliance with the protocol and complete source data verification (SDV).

In the event that the COVID-19 pandemic precludes on site visits, these will be delivered remotely in discussion with the sites.

17 ETHICAL CONSIDERATIONS

Ethical approval by a Research Ethics Committee will be needed before the trial can be started. The trial will be carried out according to guidelines of good clinical practice (GCP) as defined by paragraph 28 and Schedule 1 Part 2 of the Medicines for Human Use (Clinical Trials) Regulations, 2004, and the Clinical Trials Directive (2001/20/EC) elsewhere in the EU and follow the principles of research governance.

17.1 Patient Confidentiality

The patient's full name, date of birth, hospital number and NHS number will be collected to enable tracing through national records, if required. The personal data recorded on all records will be regarded as confidential, and to preserve each patient's anonymity, only their initials and trial number will be recorded on CRFs. The patients will be identified within the CRFs by the use of a unique trial number allocated to them upon entry into the study.

The Principal Investigator (or designee) at each site must keep a log of patients' trial numbers, names, addresses and hospital numbers. The Principal Investigator must ensure that patient confidentiality is maintained and that all trial documents (e.g. consent forms) are maintained in strict confidence.

The SCTRU will maintain the confidentiality of all patient data and will not reproduce or disclose any information by which patients could be identified. Patients will only be referred to by Trial Number and Initials in any essential trial related correspondence, including Case Report Forms.

All patient identifiable data will be handled, computerised and stored in accordance with the GDPR and Data Protection Legislation and PHS Data Protection Policy.

17.2 Informed Consent

All patients will be informed of the aims of the study, the possible adverse events, the procedures and possible hazards to which they will be exposed, and the mechanism of treatment allocation. They will be informed as to the strict confidentiality of their patient data, but that their medical records may be reviewed for trial purposes by authorized individuals other than their treating physician. It will be emphasized that the participation is voluntary and that the patient is allowed to refuse further participation in the protocol whenever they want. This will not prejudice the patient's subsequent care.

Documented informed consent must be obtained for all patients included in the study before they are enrolled or randomized. This must be done in accordance with the national and local regulatory requirements and must conform to guidelines on Good Clinical Practice. That is, "the written informed consent form should be signed and personally dated by the patient or by the patient's legally acceptable representative".

All Patient Information Sheets & Informed Consent Forms will be version controlled and dated and this information will always be stated in any communication with ethics committees.

18. DISSEMINATION, OUTPUTS, PUBLICATION POLICY AND ANTICIPATED IMPACT

All presentations and publications relating to the trial must be authorised by the Trial Management Group. The main trial results will be published in the name of the trial in a peer-reviewed journal, on behalf of all collaborators. The manuscript will be prepared by the Trial Management Group representatives from SCTRU and high accruing clinicians. The trials offices and all participating Centres and clinicians will be acknowledged in this publication. Any data that might detrimentally affect the progress of the trial will not be released prior to the end of the trial. No investigator may present or attempt to publish data concerning their patients, which is directly relevant to the questions posed in the trial, until the main results have been published.

The TMG will seek PPI input to develop a dissemination plan so that patients/caregivers understand the findings and can engage confidently with clinicians. The dissemination plan will also include a requirement to offer the results of the study and its lay summary to patients/next of kin.

19. RESEARCH GOVERNANCE

Trial Organisation

Chief Investigator – The Chief Investigator will have overall responsibility for the design, co-ordination and management of the study. These include:

- Trial authorisation including responsibility for the protocol and obtaining approvals
- Ensuring that the trial is conducted according to Good Clinical Practice (GCP)
- Assessment of SAEs and providing a prompt response as to whether the SAE is a SUSAR.

Clinical Trials Unit – The Sponsor has delegated the responsibility for overall project management, data management and monitoring to the Scottish Clinical Trials Research Unit (SCTRU), based in Edinburgh. Responsibilities include:

- Assistance with completion of the IRAS form and REC communication
- Production of trial specific documentation (i.e. CRFs)
- Assistance with site activation procedures within centres
- Data management
- Financial Management
- Monitoring
- Pharmacovigilance – Reporting of serious adverse reaction (SAR)s / SUSARs

Statistical Analysis – [name], based at SCTRU, Edinburgh will undertake the final analysis or the secondary efficacy endpoint arising for this study.

Sponsor – PHS will act as study sponsor. Central study co-ordination, data collection, monitoring and organisation of the data for the statistical analyses will be undertaken by SCTRU, which has processes in place to ensure that the study will not open to recruitment until appropriate approvals and authorisations have been obtained from the independent research ethics committee, and NHS Research and Development departments.

Local Project Teams – These will consist of oncologists (responsible for introducing the patient to the study and ensuring eligibility and consent), Research Nurse (responsibilities include patient recruitment and co-ordination of all aspects of data collection), other health care professionals and administrative staff. Centres are specifically responsible for conducting the trial in accordance with the protocol, Standard Operating Procedures (SOPs), the trial agreement and Good Clinical Practice.

20. FINANCING AND INSURANCE

This study is funded by National Institute for Health Research (NIHR) and the IMP (micronised progesterone/placebo) is provided by Besins Healthcare (UK) Ltd. Indemnity for participating hospitals is provided by the usual NHS indemnity arrangements.

Appendix 1 – The Principles of ICH Good Clinical Practice

1. Clinical trials should be conducted in accordance with the ethical principles that have their origin in the Declaration of Helsinki, and that are consistent with GCP and the applicable regulatory requirement(s).
2. Before a trial is initiated, foreseeable risks and inconveniences should be weighed against the anticipated benefit for the individual trial subject and society. A trial should be initiated and continued only if the anticipated benefits justify the risks.
3. The rights, safety, and well-being of the trial subjects are the most important considerations and should prevail over interests of science and society.
4. The available nonclinical and clinical information on an investigational product should be adequate to support the proposed clinical trial.
5. Clinical trials should be scientifically sound, and described in a clear, detailed protocol.
6. A trial should be conducted in compliance with the protocol that has received prior institutional review board (IRB)/independent ethics committee (IEC) approval/favourable opinion.
7. The medical care given to, and medical decisions made on behalf of, subjects should always be the responsibility of a qualified physician or, when appropriate, of a qualified dentist.
8. Each individual involved in conducting a trial should be qualified by education, training, and experience to perform his or her respective task(s).
9. Freely given informed consent should be obtained from every subject prior to clinical trial participation.
10. All clinical trial information should be recorded, handled, and stored in a way that allows its accurate reporting, interpretation and verification.

This principle applies to all records referenced in this guideline, irrespective of the type of media used.
11. The confidentiality of records that could identify subjects should be protected, respecting the privacy and confidentiality rules in accordance with the applicable regulatory requirement(s).
12. Investigational products should be manufactured, handled, and stored in accordance with applicable good manufacturing practice (GMP). They should be used in accordance with the approved protocol.
13. Systems with procedures that assure the quality of every aspect of the trial should be implemented.

Aspects of the trial that are essential to ensure human subject protection and reliability of trial results should be the focus of such systems.

[figure not shown]

Appendix 3 – Patient pathway

Appendix 3 – Patient pathway (Cohort 2 continued)

Appendix 4 – Stage 1: Schedule of activities

Dosing		Day 1	Day 2	Day 3	Day 4	Day 5/6/7/8/9/10 ⁵	Post-trial
Dexamethasone – non IMP	≥4mg-12mg for ≥48 hours	8mg	As clinically indicated	As clinically indicated	As clinically indicated	As clinically indicated with exception of the day progesterone is given when the dose will be 8mg	As clinically indicated
Progesterone - IMP		200mg				600mg given on one of the above days	
Activity/Day	≤ 7 days prior to progesterone						
Symptom directed physical examination	X	X					
Weight/BMI	X						
BP, pulse, temp	X						
Medical History	X						
Full blood count	X						
Clotting profile	X						
Urea and electrolytes	X						
Pregnancy check	X						
Fasting glucose	X						
Progesterone PK blood samples		X ¹				X ²	
AE review and Dex dose review		X	X	X	X	X	
Concomitant Medications Review	X	X				X ³	
CT/MRI brain ⁴	X						

¹ = At baseline (pre-dosing with progesterone); t = 1, 2, 3, 4 and 6 hours (all +/- 15 minutes); then 10 and 24 (both +/- 2 hours) after administration of progesterone.

² = At PK sampling day (one day between days 5-10) (pre-dosing with progesterone); t = 1, 2, 3, 4 and 6 hours (all +/- 15 minutes); then 10 and 24 (both +/- 2 hours) after administration of progesterone.

³ = On PK sampling day only

⁴ = CT/MRI brain – Within 14 days of screening visit

⁵ = Patients will be contacted by the Research Team 30 days after their 2nd dose of progesterone, to confirm if patient has experienced any SAEs. Patients will also be asked to contact the Research Team should they experience any side effects up to and including 30 days after their 2nd dose of progesterone (days 35-40). In addition, any events occurring more than 30 days after final IMP that are deemed to be related to the IMP should be notified to PHS by emailing [contact].

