Aim/Objective:	The overall objective is to provide (a) pharmacokinetic data to guide the dosing of micronised progesterone as a steroid-sparing agent for the treatment of patients with brain tumour oedema, (b) evidence of feasibility and (c) preliminary evidence of efficacy to underpin a subsequent definitive randomised controlled trial comparing micronised progesterone and placebo in addition to standard treatment with dexamethasone.
Study Design:	Stage 1: Single arm, pharmacokinetic/dose confirmation Stage 2: Randomised, double blind, controlled evaluation of micronised progesterone as a steroid sparing agent
Study IMP:	The IMP is micronised progesterone in Stage 1 and micronised progesterone/placebo in Stage 2.
Non IMP:	Although used in the trial, Dexamethasone is not the IMP and will be supplied from hospital stock.
Randomisation:	Randomisation will be 1:1, with stratification by clinical site (Leeds and Liverpool)
Patient Accrual:	Stage 1: 6 patients (Leeds); Stage 2: 36 patients (Leeds and Liverpool). Please note that patients in Stage 1 are excluded from participating in Stage 2. Both are separate subsets of patients and will have a separate consent form
Final Analysis:	The final analysis will be performed when all patients have completed treatment and have been followed up for one week (i.e., after 22 days)
Interim Analysis:	No interim analysis is planned
End of Study:	The end of the study is defined as the date where all patients have completed their assessments and all data has been cleaned, Quality Controlled and the database is locked for analysis.
Inclusion Criteria:	
1) Patients ≥ 18 years' old2) Capable of giving informed consent

- 3) ECOG performance status 0, 1 or 2
- 4) Clinical and/or radiological diagnosis of cerebral metastases with peritumoural oedema on CT/MRI in the last 14 days
- 5) Responding symptomatically to dexamethasone for control of brain tumour symptoms at a dose of $\geq 4\text{mg}$ - 12mg for ≥ 48 hours
- 6) Ability to swallow oral medication

Exclusion Criteria:

- 1) Patients who are unable or unwilling to give informed consent
- 2) History of unexplained vaginal bleeding
- 3) Concurrent meningioma
- 4) On HRT medication
- 5) History of venous thromboembolic disease, myocardial infarction or stroke in last 12 months
- 6) History of cholestasis in the last 6 months
- 7) History of allergy to either progesterone or other ingredients of the trial drug including peanut allergy.

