1.5.4 Micronised progesterone for administration (Utrogestran)

Details of micronised progesterone are contained in the current version of the SmPC. Of note, much of the information in the SmPC relates to the approved use of micronised progesterone in combination with oestrogen in post-menopausal women with an intact uterus at potential risk of endometrial cancer, as hormone replacement therapy.

Micronised progesterone is not taken with food in routine practice as this increases its bioavailability. The recommended daily dose is 100 mg or 200 mg daily at bedtime.

With regard to potential drug interactions, drugs known to induce hepatic CYP450-3A4 such as anti-epileptic agents (phenytoin, carbamazepine) may increase the metabolism and elimination of progesterone; ketokonazole and other inhibitors of CYP450-3A4 may increase the bioavailability of progesterone.

The incidence of adverse drug reactions with oral micronised progesterone was calculated as 1.43/1,000 patient years', corresponding to approximately 1.5 spontaneously reported cases in every 1000 patients exposed. Clinical trial data comparing micronised progesterone in combination with conjugated oestrogen to conjugated oestrogens alone or placebo suggest an excess of headache and breast tenderness in those taking micronised progesterone. Somnolence, fatigue or transient dizziness may occur 1 to 3 hours after intake of micronised progesterone and is reported to be associated with high doses of progesterone. Withdrawal vaginal bleeding may occur in women in the week following discontinuation.

Micronised progesterone is absorbed by the digestive tract and in healthy volunteers plasma progesterone levels were maximum 2.2 +/- 1.4 hours following administration. Progesterone is highly (96%-99%) protein bound, primarily to serum albumin and transcortin. Progesterone is metabolised primarily by the liver predominantly 20 α hydroxy- Δ 4 α - prenone and 5 α - dihydroprogesterone. The elimination half-life observed is 16.8 +/- 2.3 hours with urinary elimination accounting for 95% in the form of glycoconjugated metabolites. The pharmacokinetics of micronized progesterone are reported as independent of dose. Individual pharmacokinetic characteristics were maintained over several months.

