12.2 Recording and reporting of Adverse Events

All Adverse Events will be recorded in the Case Report Form and graded according to Common Terminology Criteria for Adverse Events (CTCAE) version 5. The Investigator, or delegated co-investigators, will assess each event for relatedness. Any AE considered related becomes an AR.

All adverse events that occur after the signing of written informed consent and within 30 days after the final IMP will be recorded on the appropriate eCRF page. In addition, any events occurring more than 30 days after final IMP that are deemed to be related to the IMP should be notified to PHS by emailing [contact].

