12.3 Recording and reporting of Serious Adverse Events

All serious adverse events that occur after the signing of written informed consent and within 30 days after the final IMP will be recorded on the SAE report form on the trial eCRF. The CTCAE grading will also be captured. The Investigator, or delegated co-investigators, will assess each event for relatedness. Any SAE considered related becomes a SAR.

In addition, any events occurring more than 30 days after final IMP that are deemed to be related to the IMP should be notified to PHS by emailing [contact].

The SAE case report form must be completed on the Trial eCRF and signed by the Principal Investigator, or delegated co-investigator of the centre involved, within 24 hours of the site team becoming aware of the event.

All initial SAE reports should contain the following minimum information:

- Reporter information
- At least one subject identifier (trial number/patient initials)
- Event term
- Assessment of relatedness
- Suspect drug or procedure
- Serious criteria

Sites must email [contact] to notify PHS that an SAE has been reported.

All SAEs will be forwarded to the CI by PHS for assessment of relatedness, and expectedness against the SmPC. Any SAE that is deemed to be both related and unexpected (i.e. a SUSAR) will be notified to the appropriate Competent Authorities and Research Ethics Committee within 7 days of becoming aware of the event for fatal or life threatening events and 15 days for all other serious events. An SAE will be treated as related if either the PI, CI or both consider it to be related.

Please refer to PROSPER instruction manual for sites for reporting instructions.

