⁸ Patients will be contacted by the Research Team on Day 44 to confirm if patients has experienced any SAEs. Patients will also be asked to contact the Research Team should they experience any side effects up to and including Day 44. In addition, any events occurring more than 30 days after final IMP that are deemed to be related to the IMP should be notified to PHS by emailing [contact].

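### Non-serious adverse events must be recorded to 30 days after the last IMP, but for most of that window no one is scheduled to ask about them

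*Protocol*

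**What the plan says.** - **Recording rule.** Protocol Section 12.2: "All adverse events that occur after the signing of written informed consent and within 30 days after the final IMP will be recorded". Section 12.3 sets the same window for SAEs: "All serious adverse events that occur after the signing of written informed consent and within 30 days after the final IMP will be recorded". Section 12.1 defines an AE as any untoward medical occurrence, with or without a causal link to the IMP. Section 12.2 leaves the judgement of relatedness to the investigator.
- **Stage 1 (Appendix 4).** The row "AE review and Dex dose review" is marked on Days 1 to 4 and in the Day 5-10 column, and is blank under the post-trial column. The second IMP dose is "600mg given on one of the above days", that is, on one of Days 5 to 10. Footnote 5 adds: "Patients will be contacted by the Research Team 30 days after their 2nd dose of progesterone, to confirm if patient has experienced any SAEs". The next sentence of that footnote asks patients to get in touch if they have side effects over the same 30 days.
- **Stage 2 (Appendix 5).** AE review takes place on alternate days to Day 14 and during Days 15-21, and again on Day 22. The daily side-effect diary also runs to Day 22. Footnote 8: "Patients will be contacted by the Research Team on Day 44 to confirm if patients has experienced any SAEs". It too is followed by a request that patients report side effects, up to Day 44.
- **Timing of the analysis.** The Trial Summary places the final analysis when patients have completed treatment and been "followed up for one week (i.e., after 22 days"). The final-analysis section waits until the end of study has been declared. The end-of-study section defines that as assessments complete, data cleaned and database locked.

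**The concern.** The rule in Section 12.2 makes no distinction between serious and non-serious events, but the means of collection does. Once scheduled review ends, SAEs are actively asked about at the close of the window, while non-serious events rely on unsolicited self-report. The footnotes also ask patients about side effects. A patient who puts a symptom down to the tumour, to dexamethasone or to another medicine may reasonably not call, although Section 12.1 makes that symptom an AE. The patient is in effect asked to judge causality before the investigator can.

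Stage 1 is the more exposed of the two. It has no side-effect diary, and it is where this population first receives 600 mg, before repeated dosing in Stage 2. At stake is whether the late safety record is complete by the protocol's own rule, in a trial whose Stage 2 primary aim includes safety.

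**Working it through.** **Inputs.** Recording window: 30 days after the last IMP (Section 12.2). Last IMP: Day 5 to Day 10 in Stage 1 (Appendix 4), Day 14 in Stage 2 (Section 11.3). Last scheduled AE review: Day 10 at the latest in Stage 1, Day 22 in Stage 2. Day 14 assumes that the patient completes treatment.

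**Step 1: reproduce the protocol's own window.** Close of window = last IMP day + 30.
- Stage 1: 5 + 30 = 35 to 10 + 30 = 40. Footnote 5 gives days 35-40, so it agrees.
- Stage 2: 14 + 30 = 44. Footnote 8 gives Day 44, so it agrees.

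The windows in Section 12.2 and in the appendices are therefore consistent. The difference lies in how events are collected within them.

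**Step 2: days in the window after the last scheduled AE review.** Days = close of window − last review day.

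| Stage | Last IMP | Last review | Window closes | Days without scheduled review | Share of 30 |
|---|---|---|---|---|---|
| 1, second dose Day 5 | 5 | 10 | 35 | 35 − 10 = 25 | 83% |
| 1, second dose Day 10 | 10 | 10 | 40 | 40 − 10 = 30 | 100% |
| 2 | 14 | 22 | 44 | 44 − 22 = 22 | 73% |

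The Stage 1 rows take the merged Day 5-10 column to mean that review continues to Day 10 whatever the dosing day. If it means review on the dosing day only, the figure is 30 days for every Stage 1 patient.

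**Step 3: routes open in those days.**
- SAEs: the closing contact by the research team, plus self-report.
- Non-serious AEs: self-report of side effects only.
- Days with no route at all for a non-serious event: 0 in both stages.

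**Step 4: the 24 h sample in Stage 1.** The sample falls on dose day + 1.
- First dose: 1 + 1 = Day 2, which already has AE review.
- Second dose: Day 6 to Day 11. Days 6 to 10 lie inside the merged column. Day 11 (dosed on Day 10) has no day column of its own, and the post-trial column carries no AE review mark. The sample itself is specified in footnote 2. Only the AE review at that visit is left unstated.

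**Step 5: analysis timing.** 44 − 22 = 22 days between the Trial Summary's one-week follow-up point and the close of the Stage 2 safety window.

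**The case against.** The strongest reply is that nothing is contradicted. Section 12.2 fixes which events are recorded and for how long, and does not require active questioning. Both footnotes give patients a way to report side effects to the last day of the window. That stands: the documents do not support saying that non-serious harms are missed, only that they may be. It does not dispose of the point, because the self-report route is both unsolicited and narrower than the AE definition, while a call on the closing day is already planned.

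Four stronger inferences are tempting and should not be drawn.

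- **Withdrawal bleeding goes unobserved.** Section 1.5.4 says "Withdrawal vaginal bleeding may occur in women in the week following discontinuation". After the repeated dosing of Stage 2 that week is Days 15-21, which has alternate-day review and a daily diary. Only a Stage 1 patient dosed late would have that week outside scheduled review. Section 1.5.4 is general product information and does not say that it applies to a single dose.
- **Acute effects of 600 mg escape notice.** The somnolence, fatigue and dizziness named in Section 1.5.4 occur 1 to 3 hours after intake. Patients are then being sampled, on a day in a column marked for AE review.
- **The primary endpoint is biased in favour of progesterone.** Stage 2 tolerability is judged to the end of the 14-day treatment period, when review is on alternate days and the diary is daily. The Stage 2 dose is chosen on pharmacokinetic exposure. Stage 2 is also double-blind. If late events are captured with the same probability *s* in both arms, the expected observed difference is *s* times the true one, which is smaller but not reversed.
- **The analysis will start with safety windows still open.** At one patient per month at each of two sites, 2 × 22/30 ≈ 1.5 patients would be between Day 22 and Day 44. That follows only if the Trial Summary is read alone. The final-analysis and end-of-study sections require completed assessments and a locked database, and Section 4.3 allots three months for final data collection, cleaning and lock.

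**Conclusion.** The point holds as a gap between the recording rule and the way late non-serious AEs are collected. After scheduled review ends, for 22 of 30 days in Stage 2 and 25 to 30 of 30 in Stage 1, these events reach the record only if the patient volunteers what he or she takes to be a side effect. Under-recording is possible. Its size cannot be estimated, because the documents give no rate of late AEs and no reporting probability. The count of days measures the exposed period, not the number of events lost.

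The conclusion assumes that the SAE-only wording of the two contacts will be followed as written. A site that asks about everything on that call would already comply with Section 12.2. The 14-day tolerability endpoint and the choice of Stage 2 dose are unaffected. The Trial Summary's 22-day phrase is a minor inconsistency of wording. The change is worth making because it is cheap and brings the safety record into line with the protocol's own rule.

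**What to change.** 1. Reword footnote 5 of Appendix 4 and footnote 8 of Appendix 5 so that the planned contact asks about all AEs since the last review, not only SAEs. The self-report request should refer to any new or worsening symptom or event, whatever its suspected cause.
2. In Appendix 4, state that AE review takes place at the 24 h pharmacokinetic sample after the second dose, including Day 11 for a patient dosed on Day 10.
3. As a wording correction, amend the final-analysis entry in the Trial Summary so that analysis follows the last patient's Day 44 contact, as the final-analysis and end-of-study sections already imply.

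**Cost.** A few minutes per patient on a contact and a visit that already exist, and revised footnotes. Against the Trial Summary's wording, the earliest analysis date moves by at most 22 days. Against the other sections and the three-month data phase it should not move.
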